2.1 Objectives & Hypotheses	<h3>2.1 Objectives and Aims</h3> 
Aims
 
1. To evaluate the determinants of Sustained Virologic Response (SVR) in patients treated with grazoprevir and elbasvir in the presence of immunosuppression (post-renal transplant). 
Primary Objective
 
1. To determine the difference in the host immune response as measured by interferon stimulated gene (ISG) expression (IP-10 in particular), and HCV specific T-cell response in post-renal transplant patients compared to historical, non-transplant patients and its association with SVR.2. To examine the efficacy of grazoprevir and elbasvir in patients post- renal transplantation compared to historical, non-transplant patients. 
Secondary Objectives
 
1. To evaluate the safety and adverse events of grazoprevir and elbasvir post-renal transplant patients compared to historical, non-transplant patients.2. To describe the effects of chronic HCV treatment on two-year renal allograft outcomes in patients treated after renal transplantation. <h4>2.1.1 Clinical hypotheses</h4> 
Primary Hypotheses
 
1. Patients treated for chronic HCV with grazoprevir and elbasvir after renal transplantation will maintain a robust host immune response as measured by ISG expression (IP-10 in particular) and HCV specific T cell responses in the presence of immunosuppression.2. The proportion of patients who achieve SVR12 will be greater than 90% in post-renal transplant patients. 
Secondary Hypotheses
 
1. The safety, tolerability, and adverse events of treatment with grazoprevir and elbasvir in patients with chronic kidney disease will not be significantly different in post-transplant patients compared to non-transplant patients.2. The treatment of chronic HCV using grazoprevir and elbasvir will improve the renal allograft outcomes in terms of rejection or graft survival. <h4>2.1.2 Clinical Impact</h4> 
Chronic HCV in patients with CKD is associated with an increased risk of death as well as renal transplant graft failures (1). With the FDA approval of grazoprevir and elbasvir, we now have a regimen that can be used in these patients with severe CKD. However, it remains unknown if there is an immunologic advantage for both achievement of SVR 12 and renal allograft outcomes in treating these patients prior to their transplant compared to waiting until after transplantation when they will be immunosuppressed. And while we predict that transplant recipients will maintain high rates of SVR, it is uncertain whether these immunosuppressed transplant recipients will maintain robust host immune responses to HCV treatment.

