2.5.2 Host Response Measurement

Determination of Interferon stimulated gene expression associated with HCV suppression

PCR. ISG expression rapidly shuts down with initiation of DAA therapy in HCV infected subjects. We would like to evaluate the effectiveness of the host response to DAA therapy in pre- and post-transplant (immunosuppressed) patients by evaluating the changes in ISG expression observed in the two groups of patients before and 4 weeks after completion of HCV therapy.

Expression analysis of select genes will be performed with predesigned or custom TaqMan assays individually or assembled into custom-designed 96-well plates or 384-well microfluidic cards (Life Technologies). Total RNA isolated from paxgenes will be reverse transcribed using random primers with the High Capacity cDNA Reverse Transcriptase Kit (Life Technologies). 1–25 ng RNA will be used for each qRT-PCR reaction. Gene expression will be determined as Ct based on 40 PCR cycles. For statistical analysis,

undetectable expression will be assigned a minimal detectable level with Ct of 40. Expression of *GAPDH* will be used as an endogenous control. Relative expression of targets normalized by *GAPDH* expression (ΔCt) will be calculated as $Ct_{GAPDH} - Ct_{\text{target}}$, with conversion and display relative to *GAPDH* expression by $2^{\Delta Ct}$. $\Delta\Delta Ct$ values, used to calculate changes in expression between samples or groups of samples, will be calculated as $\Delta Ct_{\text{sample A}} - \Delta Ct_{\text{sample B}}$, then converted to a fold change by $2^{-\Delta\Delta Ct}$. Relative expression of individual ISGs FNs in blood will also be calculated as a percent of the sum of the total measured ISGs ($[2^{\Delta Ct} \text{ of each individual ISG} / \text{total } 2^{\Delta Ct} \text{ of all measured ISGs}] \times 100$). 384-well microfluidic cards will be run on a 7900HT Fast Real-Time PCR System (Life Technologies).

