Cytokine and Chemokine ELISA. IP-10 is the most studied soluble ISG that has been associated with response to therapy. The expression of IP-10 is rapidly shut down with initiation of DAA therapy in HCV infected subjects and a higher pre-treatment IP-10 level has been associated with a poorer response to therapy. We would like to evaluate the effectiveness of host response to DAA therapy in pre- and post-transplant (immunosuppressed patients) by evaluating the fold changes in IP-10 and other proinflammatory/chemotactic cytokine expression observed in the two groups of patients before and 4 weeks after completion of HCV therapy.

Whole blood will be allowed to clot in for at least 60 minutes prior to centrifugation at 1,700 g for 15 minutes. Serum will be collected and aliquoted prior to freezing at -80°C. After thawing, serum will be centrifuged at 1,450 g for 10 minutes, and the supernatant will be used for ELISA. Quantitation performed with multiplex (Chemokine 9-plex, Proinflammatory 9-plex) assays that include CXCL10 (MesoScale Discovery). Plate-to-plate variability of pooled samples will be used for normalization across experiments. All samples will be run as technical duplicates, and averages will be used for data analysis.

Determination of HCV specific CD4 and CD8 T cells by ELISPOT

We have previously described an augmentation of HCV-specific T-cell responses with DAA therapy being associated with achieving an SVR 12. HCV specific T-cell phenotype and function will be characterized as previously described and measured before and at SVR 12.

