
2.7 Statistical Analysis and Sample Size Justification
	
Data analysis will be completed by the study biostatistician.
 
Primary Endpoints
 
Primary Objective 1. The primary endpoint for this objective will be the measurement of host immune responses using ISG expression including IP-10 levels, and HCV specific T-cell responses. ISG expression and IP-10 levels will be measured before and 4 weeks after completion of therapy. HCV specific T-cell responses will be measured before and during SVR 12 (12 weeks after completion of the study medications).
 
Primary Objective 2. The primary endpoint for this objective will be the measurement of SVR 12. This will be measured at study week 24/28, or 12 weeks after completion of the study medications.
 
Secondary Endpoints
 
Secondary Objective 1. We will assess the safety of the medications using adverse event monitoring. The primary endpoint for this objective will be the presence of any severe adverse event. A secondary endpoint will be the early discontinuation of the study medications. This will be assessed at the study visits weeks 0, 4, 8, and 12. Based upon prior trials with these investigational drugs, we estimate rate of serious adverse events of about 15% (17).
 
Secondary Objective 2. The primary endpoint for this objective will be episodes of rejection and graft survival for post-transplant patients after treatment and will be recorded via medical record abstraction as part of their enrollment in the ongoing prospective cohort study to assess treatment efficacy in chronic hepatitis C (HP – 00063362).
 
Research data will be collected and managed using REDCap (Research Electronic Data Capture) hosted at the University of Maryland, which is a secure, web-based application to support data capture for research studies. All of these variables will be entered into REDCap by study staff at the end of each study visit based upon the labs obtained, patient questionnaires, and interim records reviews, and after the initial 30 to 34 weeks of the study based upon medical records reviews.
 
Statistical Methods
 
Clinical treatment arm
 
All statistical analyses will be based on an intention-to-treat model, including all enrolled patients who received at least one dose of study medication. Both the primary efficacy and safety endpoints will be based on the proportion of patients with SVR 12 and severe adverse events, respectively, with point estimates and 95% confidence interval. Both primary efficacy and safety endpoints will be compared to a non-transplant, HCV-infected historical control group by using two-sided, exact one-sample binomial test at a significance level of 0.05. Demographic and baseline characteristics will be summarized using standard descriptive statistics overall and by patient cohort. Univariate logistic regression will be performed to identify baseline factors associated with SVR 12 at a significance level of 0.05.
 
Measurement of host immune response

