
	
Mann-Whitney or Wilcoxon matched-pairs signed rank test will be used for 2-group comparisons, and a linear mixed-effects model will be used for multigroup longitudinal comparisons with fixed effects for group (SVR versus relapse), time, and group/time interaction. A significant group/time interaction would indicate that the 2 groups had different patterns over time. A class variable will be used for time to allow an arbitrary average time pattern within a group. In addition to fixed effects summarizing average group responses over time, the model will accommodate random, patient-specific deviations in intercept and time effects. Correlations will be assessed by nonparametric Spearman rank correlation. Spotfire S+ 8.2 (TIBCO), Prism 6.0 software (GraphPad), and SAS 9.3 (SAS Institute, Inc.) will be used for statistical analysis and data presentation using a p-value of 0.05 to indicate statistical significance.
 
Power/Sample Size:
 
This is a pilot, prospective clinical trial comparing the host immune response using ISG expression, including IP-10 levels, and HCV specific T-cell responses between a historical, non-transplant cohort of 25 patients from IRB approved studies previously conducted at the IHV and post-renal transplant (immunosuppressed) patients and its association with SVR 12. The study team will perform an interim data and safety evaluation for the efficacy, safety, and tolerability of grazoprevir and elbasvir therapy. Data analysis will focus on the clinical efficacy endpoint of SVR 12 with secondary analysis looking at the relationship of the host immune response markers with the primary endpoint of SVR 12 in both groups.
 
We anticipate enrollment of 25 patients in this arm of the study. This will be compared to a historical control group of 25 patients with stored blood samples from previous IRB approved clinical trials conducted at the IHV.
 
We anticipate a SVR 12 of greater than 90% in the grazoprevir plus elbasvir treatment group post-renal transplantation. With 50 participants (25 in this study and 25 historical controls), the study will be able to estimate the difference in SVR12 proportions to within ± 0.18 (Table 2). Table 2 shows a substantial gain in precision by increasing the sample size from 15 per arm to 25 per arm; however, the effect diminishes beyond 25.
 
Table 2: Sample Size Calculation for SVR12
 
  
 N per arm	15	20	25	30	50	
   
 Accuracy to within \pm	0.24	0.20	0.18	0.17	0.13	
  
	N per arm	15	20	25	30	50	Accuracy to within \pm	0.24	0.20	0.18	0.17	0.13

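### The longitudinal model for the immune endpoints compares SVR with relapse and has no cohort term, so the transplant-versus-historical difference in Primary Objective 1 has no clearly assigned analysis and no confidence interval

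*Combined protocol and SAP*

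**What the plan says.** Primary Objective 1 (section 2.1) concerns the difference in ISG expression, IP-10 and HCV-specific T-cell response "in post-renal transplant patients compared to historical, non-transplant patients and its association with SVR". The cohort difference comes first and the association second. Primary Hypothesis 1 (section 2.1.1) is that treated transplant recipients "will maintain a robust host immune response as measured by ISG expression (IP-10 in particular) and HCV specific T cell responses" under immunosuppression. The Power/Sample Size text in section 2.7 again gives the comparison with 25 historical patients as the purpose of the trial.

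The methods are in section 2.7, Measurement of host immune response. First, "Mann-Whitney or Wilcoxon matched-pairs signed rank test will be used for 2-group comparisons"; the groups, markers, visits and summary measure are not named. Second, a linear mixed model is specified "with fixed effects for group (SVR versus relapse), time, and group/time interaction", with patient-level random intercept and time effects and a 0.05 significance threshold.

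Section 2.5.2 adds detail by assay. For ISG expression it speaks of "evaluating the changes in ISG expression observed in the two groups of patients before and 4 weeks after completion of HCV therapy", and for IP-10 of "evaluating the fold changes in IP-10 and other proinflammatory/chemotactic cytokine expression observed in the two groups of patients"; in both, the two groups are pre- and post-transplant patients. For T cells it says only: "HCV specific T-cell phenotype and function will be characterized as previously described and measured before and at SVR 12".

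For SVR12 and severe adverse events, section 2.7 (Clinical treatment arm) plans proportions "with point estimates and 95% confidence interval". It plans no interval for the immune markers.

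**The concern.** A model whose only grouping factor is treatment outcome says nothing about a difference between cohorts. If it is run as the main immune analysis, the first question of Primary Objective 1 goes unanswered. The rank test could fill the gap, but the analyst would have to decide afterwards that the two groups are the cohorts. For T cells the analyst would also have to choose between the baseline value, the post-treatment value and the change.

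Two misreadings are then likely. A non-significant rank test between cohorts could be taken as evidence that the response is maintained, although only an interval shows which differences remain possible. A non-significant SVR-by-time interaction could be taken as evidence of no link between immune response and SVR, when it may only reflect a handful of failures.

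**Working it through.** **What each method answers**

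| Question | Method in section 2.7 | What is missing |
|---|---|---|
| Cohort difference, ISG | Mann-Whitney, by inference from section 2.5.2 | Link to cohort; CI |
| Cohort difference, IP-10 | Mann-Whitney, by inference from section 2.5.2 | Link to cohort; CI |
| Cohort difference, T cells | Mann-Whitney at most | Link to cohort; change variable; CI |
| Association with SVR | Mixed model, SVR versus relapse | Group for other non-SVR patients; CI |

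**The plan's own figure.** No precision or power figure is given for an immune marker. The only sample-size figure is ±0.18 for the SVR12 difference at 25 per arm. It reproduces as 1.96 × √(0.90×0.10/25 + 0.85×0.15/25) = 0.183 if the unstated historical rate is taken as 0.85 (assumption). The present point does not depend on it.

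**Inputs.** There are 25 transplant and 25 historical patients, and anticipated SVR12 is above 90% (section 2.7, Power/Sample Size). The cited CKD stage 4/5 study reported 94% by intention to treat (section 2.2). Each marker has two endpoint visits (section 2.7, Primary Endpoints). The documents give no marker SD, so results are in SD of change. A two-sided 5% level, normal changes and equal variances are assumed.

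**Expected failures**
- Trial arm, n = 25: 25 × 0.10 = 2.5 at 90% SVR; 25 × 0.06 = 1.5 at 94%.
- Probability of none in 25: 0.90^25 = 0.072; 0.94^25 = 0.213.
- Both cohorts, n = 50, if the historical rate is the same (not stated): 5 and 3 expected; probability of none 0.90^50 = 0.005 and 0.94^50 = 0.045.

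These counts cover all non-SVR patients, so relapses cannot exceed them.

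**Precision.** With two complete visits, the group-by-time interaction is a comparison of mean change. The half-width is t(0.975; n1+n2−2) × √(1/n1+1/n2). The last column is the difference detectable with 80% power (noncentral t).

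| Contrast | Sizes | t × root term | CI half-width (SD) | Detectable (SD) |
|---|---|---|---|---|
| Cohort | 25 v 25 | 2.011 × 0.283 | 0.57 | 0.81 |
| SVR status, 90%, both cohorts | 45 v 5 | 2.011 × 0.471 | 0.95 | 1.35 |
| SVR status, 94%, both cohorts | 47 v 3 | 2.011 × 0.595 | 1.20 | 1.70 |
| SVR status, trial arm only | 23 v 2 | 2.069 × 0.737 | 1.53 | 2.16 |

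**Power at an illustrative 0.8 SD.** The cohort contrast has 79%. The SVR-status contrast, averaged over the binomial number of failures and counting zero failures as no power, has 37% (90% SVR) or 25% (94%) in 50 patients. In 25 patients it has 20% or 13%.

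**The case against.** The strongest reply is that the sections are meant to be read together. Section 2.5.2 identifies the two groups as pre- and post-transplant patients and gives change in ISG expression and fold change in IP-10 as the quantities. Section 2.7 then supplies Mann-Whitney, and the mixed model serves the second half of the objective. For ISG and IP-10 this is the natural reading and it stands. Little efficiency would be lost: on simulated normal data at 0.8 SD with 25 v 25, Mann-Whitney on change has 77% power against 79% for the cohort-by-time test. A reader might infer that the plan has no analysis of the cohort difference at all; the documents do not support that.

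Nor do they support saying that no effect measure exists. Section 2.5.2 defines a fold change between groups of samples for ISG expression and mentions fold changes in IP-10. What is missing throughout is the interval, and for T cells the change variable as well.

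Primary Hypothesis 1 names no comparator, and the within-patient Wilcoxon test bears on change inside the transplant cohort. That is fair. The need for a between-cohort interval comes from Primary Objective 1.

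The few failures matter less if the association is only secondary, as the Power/Sample Size text calls it in this pilot. But section 2.1 places the association inside a primary objective, so its status is not settled.

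A reader might also infer that the mixed model cannot be fitted with two visits per marker. That would go too far. With one value per visit, a correlated random intercept and time effect plus residual has four variance parameters against three moments. However, the covariance structure is not stated, an independent intercept plus a 0/1 time contrast is just identified, and the fixed interaction is estimable under a simpler structure.

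**Conclusion.** The point holds in a limited form. As written, the longitudinal model does not estimate the contrast that Primary Objective 1 names first. A usable rank test is available for ISG and IP-10 but is not tied to the cohorts. The T-cell response lacks a change variable, and no immune marker has a planned confidence interval.

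The contrast that is modelled is the less informative one. Its half-width is 0.95 to 1.20 SD of change with both cohorts pooled, against 0.57 SD between cohorts, and it leaves non-SVR patients other than relapsers without a group. That sits poorly with the intention-to-treat set of all dosed patients.

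The structural part rests on the text alone. The figures assume normal changes with equal variances, complete data at both visits and, for the pooled counts, a historical SVR rate equal to the trial's. This should be corrected before analysis, but it does not make the trial uninterpretable.

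**What to change.** 1. Name cohort (transplant versus historical) by time, equivalently the between-cohort difference in change, as the Objective 1 analysis for ISG expression, IP-10 and T-cell response, each at its own two visits. Fix the scale in advance, for example log or delta-Ct. Define T-cell change as the SVR12 visit minus baseline.
2. Report each difference with a 95% CI. Choose the method for each marker in advance; where a rank test is used, give the Hodges-Lehmann shift with its CI.
3. If a mixed model is used, specify a random intercept or an unstructured two-visit covariance.
4. Keep the marker-SVR association as a separate analysis of SVR versus non-SVR, with estimates, CIs and a statement of its limited precision. Reconcile whether it is primary (section 2.1) or secondary (section 2.7, Power/Sample Size).
5. Optionally, add a baseline-adjusted estimate as a sensitivity analysis, because the cohorts are not randomised.

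The cost is SAP wording and a little more analysis work, with no further trial patients or visits. The intervals will be wide. The comparison also requires stored historical samples at the same time points; the documents do not state that these exist, so this should be confirmed first.

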A recent study (C-SURFER) evaluated the safety and efficacy of 12 weeks of grazoprevir and elbasvir for HCV genotype 1 patients with CKD stages 4/5. The study was designed to randomize eligible patients to either immediate or deferred treatment with grazoprevir and elbasvir. The delayed treatment arm received placebo and was treated with grazoprevir and elbasvir subsequently. The study participants were HCV genotype 1, CKD stages 4/5 (eGFR <30), and 76% were on hemodialysis, and 46% were African Americans. A small number of patients with compensated cirrhosis were allowed. The study reported an intention to treat (ITT) and modified ITT analysis of 94% and 99% for SVR12. There were no changes in hemoglobin or other adverse events or erythropoietin use in the immediate treatment group compared to placebo. Four percent of patients in the deferred treatment group discontinued treatment due to an adverse event, mainly headache, nausea or fatigue (17). In summary, a regimen of grazoprevir and elbasvir could be an effective regimen to treat HCV genotype 1 infection in patients with severely compromised renal function.

While studies evaluating the safety and efficacy of this regimen in patients with chronic kidney disease have shown success with few adverse events, little is known about the efficacy of this, or any other, therapy in patients on immunosuppression after renal transplantation or whether it is optimal to treat hepatitis c before or after transplantation. Because waiting until after transplant to treat patients for HCV is advantageous by allowing those patients to receive HCV-positive donor organs, most centers are waiting to treat these patients. In order to observe whether there is any difference immunologically or clinically in treating patients before or after renal transplantation, we will compare our transplant cohort to a cohort of historical, non-transplant patients treated for HCV in whom we have stored blood samples from prior IRB-approved studies.

Significance

The prevalence of chronic hepatitis C in patients with CKD is much higher than that observed in the general population (18). This highlights the importance of finding a ribavirin free regimen that is not excreted through the kidneys. However, it is unclear what the timing of HCV therapy should be for these patients.

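### SVR12 in all dosed transplant patients is set against controls picked for having stored blood, so losses to follow-up may count in one group and not in the other

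*Combined protocol and SAP*

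**What the plan says.** For the transplant cohort, section 2.7 (Statistical Methods, Clinical treatment arm) states: "All statistical analyses will be based on an intention-to-treat model, including all enrolled patients who received at least one dose of study medication". It gives no rule for a missing SVR12 result. Efficacy and safety are then compared with a non-transplant historical control group by a two-sided exact one-sample binomial test at 0.05.

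The controls are described twice, both times by sample availability. Section 2.2 calls them "a cohort of historical, non-transplant patients treated for HCV in whom we have stored blood samples from prior IRB-approved studies". Section 2.7 (Power/Sample Size) says "This will be compared to a historical control group of 25 patients with stored blood samples", and the same paragraphs count these 25 in the precision of the SVR12 difference (±0.18 with 25 per arm).

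The immune endpoints need blood taken after treatment. Section 2.7 (Primary Endpoints) states: "ISG expression and IP-10 levels will be measured before and 4 weeks after completion of therapy". HCV-specific T cells are measured before therapy and 12 weeks after it. Section 2.5.2 makes the ISG and IP-10 change a comparison "observed in the two groups of patients before and 4 weeks after completion of HCV therapy".

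The plan does not say which time points the control samples cover, which regimen the controls received, or how their SVR12 denominator is formed.

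**The concern.** One set of 25 controls serves two purposes with different needs. For the immune comparison, a control is useful only if post-treatment blood was stored. For SVR12, the right comparator is everyone who started treatment. A historical patient who died or was lost before the sampling visits cannot supply the blood and would tend not to be chosen. A transplant patient with the same course remains in the denominator. Matching or adjusting on baseline characteristics would not remove this, because the selection acts on follow-up.

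Primary Objective 2 is this comparison, and section 2.2 says the study should help clinicians decide whether to treat before or after transplant. A shortfall produced by different denominators could be read as an effect of immunosuppression.

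**Working it through.** **Inputs from the documents.** Transplant cohort n = 25; controls n = 25; two-sided exact one-sample test at 0.05; anticipated transplant SVR12 above 90%; no control rate stated. The only figures showing how the analysis set changes SVR12 are those for the cited trial in CKD stages 4/5: "The study reported an intention to treat (ITT) and modified ITT analysis of 94% and 99% for SVR12". The exclusions behind its modified ITT figure are not described.

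**1. The plan's own figure.** The 95% half-width for a difference is 1.96 × √[(p1(1−p1) + p2(1−p2))/n].
- 0.90 in both arms: 1.96 × √(0.18/25) = 0.166, which is not the stated value.
- 0.90 and 0.85: 1.96 × √(0.2175/25) = 0.183. This pair reproduces all five entries of Table 2 (0.24, 0.20, 0.18, 0.17, 0.13). So does 0.875 in both arms.

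Table 2 therefore does not fix the control rate, and is compatible with one below 0.90.

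**2. Size of the artificial gap.** Assume SVR12 is 99% among patients followed to the visit and missing counts as failure. With a proportion d lost, the all-dosed rate is 0.99 × (1−d):
- d = 2%: 97.0%, gap 2.0 points
- d = 5%: 94.05%, gap about 5 points
- d = 10%: 89.1%, gap 9.9 points

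**3. Effect on the planned test (scenario).** Let the true all-dosed SVR12 be 94% in both groups, and let the selected controls have a true rate of 99%. The one-sample test takes the observed control rate as its null. Rejection limits below are for the minimum-likelihood version of the test.

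| Controls with SVR12 | Reject low if transplant responders ≤ | Chance of that at 94% | Chance of this control result at true 94% | at true 99% |
|---|---|---|---|---|
| 25/25 | 24 | 78.7% | 21.3% | 77.8% |
| 24/25 | 21 | 6.0% | 34.0% | 19.6% |
| 23/25 | 20 | 1.5% | 26.0% | 2.4% |

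Summing over all control results:
- Unselected controls (true 94%): rejection in 21.0% of trials, of which 19.2% find the transplant cohort worse. The 25/25 row alone gives 0.213 × 0.787 = 16.8%.
- Selected controls (true 99%): rejection in 62.4%, all but a negligible part finding the transplant cohort worse. The 25/25 row gives 0.778 × 0.787 = 61.2%.

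The doubled-tail version gives 20.3% and 62.4%, so the choice between versions hardly matters here.

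**4. Separating the two causes.** The 21% occurs with no selection at all. It comes from using a rate estimated in 25 patients as a known constant: with 25/25 controls responding, one transplant failure is enough to reject. Selection accounts for the rise from 21% to 62%. With a two-sample Fisher test the corresponding rates are about 0.2% in both cases. That removes the false declarations but leaves the 5-point bias in the estimated difference.

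**The case against.** The strongest reply is that the documents establish the asymmetry but not its consequences.

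- A reader might infer that the controls are in effect completers. The documents do not say so. They give no control sample times and do not require every control to have both post-treatment samples. Section 2.5.2 still calls the two groups pre- and post-transplant, and the T-cell timing is not tied explicitly to the controls. Attending follow-up is not completing treatment: in this trial, patients who stop early are still seen at post-treatment weeks 4 and 12. Nor is it SVR: relapse is a modelled group in section 2.7.
- A reader might infer that the safety comparison is tilted too. Section 2.7 does not say that the safety comparator is these 25; its one safety figure, about 15% serious adverse events, comes from prior trials. Whether patients who stopped for adverse events lack samples is also unknown.
- A reader might set the rejection rate against a fixed 94% (1.5%) beside that against a fixed 99% (45% minimum-likelihood, 19% doubled-tail) and blame selection for the whole rise. That treats the control rate as known, although the plan would estimate it from 25 patients.
- This is a pilot with stated precision of ±0.18, and a 5-point gap is under a third of that.

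All four limit what can be said about direction and size. None supplies a common denominator or a missing-data rule, and low precision does not excuse an avoidable bias in a primary comparison that will be formally tested.

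**Conclusion.** The point holds as an asymmetry of analysis sets: all dosed patients on one side, patients with stored blood on the other, with nothing in the plan to reconcile them. Taken alone it works against the transplant cohort, provided that a missing SVR12 counts as failure there. The net direction is not established, because the control regimen and case mix are unstated and could offset it.

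The size is unknown. The rise from about 21% to about 62% in false declarations is a scenario. It assumes equal true all-dosed rates of 94%, that the cited trial's modified ITT figure of 99% can stand for controls selected on stored blood, and that the observed rate in 25 controls is the null value. The documents do not support describing the controls as completers, nor a definite tilt in the safety comparison.

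**What to change.** Separate the two uses of the control group in section 2.7.

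- **SVR12:** take the control rate from all patients who received at least one dose in the source historical trials, whether or not blood was stored.
- **Missing SVR12:** state one rule, for example missing equals failure, and apply it to both groups.
- **Adverse events:** say which group is the comparator. If it is these controls, use the same all-dosed set.
- **Test:** replace the one-sample test by a two-sample comparison with a confidence interval for the difference, so that uncertainty in the control rate is counted.
- **Immune endpoints:** keep the 25 patients with stored samples for ISG, IP-10 and T-cell comparisons only, and state which sample time points they must have.

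If only the 25 can be used, make the stated SVR12 comparison one between patients followed to the SVR12 visit in both groups, and report the all-dosed transplant rate with its confidence interval descriptively.

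The cost is a wording change and retrieval of SVR12 (and, if needed, adverse-event) totals from the institution's earlier trials. It assumes those totals are available, which the documents do not show. No new patients or tests are needed.
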